7.4 Full Analysis Immunogenicity Set (FAS)

All subjects in the All Enrolled Set who are randomized, receive a study vaccination AND provide immunogenicity data at relevant time points

- Days 1 and 29 (Immunogenicity FAS-1).
- Days 1 and Day 8 (Immunogenicity FAS-2), or Day 181 (Immunogenicity FAS-3).

Subjects in the FAS will be analyzed according to the vaccine to which they were randomized. In case of vaccination error, subject in the FAS will be analyzed “as randomized” (i.e., according to the vaccine a subject was designated to receive, which may be different from the vaccine the subject actually received).

If a subject is unblinded during the study, he/she will be included in the FAS.

7.5 Per Protocol Immunogenicity Set (PPS)

All subjects in the FAS Immunogenicity who:

- Have serology results available.
- Correctly receive the vaccine (i.e., receive the vaccine to which the subjects is randomized and at the scheduled time point Day 1).
- Have no major protocol deviations leading to exclusion (see section 6.2) as defined prior to unblinding / analysis.
- Are not excluded due to other reasons defined prior to unblinding or analysis (see section 6.2)

In case of vaccination error, the subject is excluded from the PPS. If a subject receives a vaccine, labeled for another subject but the same as the one the subject was randomized to, the subject will not be removed from the PPS.

If a subject is unblinded during the study, except for SUSAR, he/she will be excluded from the PPS.

7.6 Other Analysis Sets

All subjects in the All Enrolled Set who consent to additional blood draws, receive a study vaccination AND provide exploratory assay data at relevant time points will be included in an exploratory assay subset. The analyses of the exploratory endpoints will be detailed in a separate statistical analysis plan.

7.7 Overview of Analysis Sets by PD Code

Table mock-ups with summaries of the number of available subjects by objective and analysis set are given below.

Table 7.7-1: Safety Sets

PD code	PD Description	All Exposed Set	Overall Safety Set	Unsolicited Safety Set	Solicited Safety Set			
					T30m	D1-D4*	D5-D8	D8-D14
	Exclusion code	EXPFL	SAFFL	SSU10FL	SSS01FL	SSS02FL	SSS03FL	SSS04FL
100	Study vaccine not administered AT ALL	EXC	EXC	EXC	EXC	EXC	EXC	EXC
115	Subject did not provide any post-vaccination unsolicited safety data	None	None	EXC	None	None	None	None
116	Subject did not provide any post-vaccination solicited safety data	None	None	None	EXC	EXC	EXC	EXC

EXC = excluded from this analysis set.

* Without 30 minutes post-vaccination.

All Safety sets and codes correspond to the primary safety objective.

Table 7.7-2: Immunogenicity Sets

PD code	PD Description	PPS	FAS-2		FAS-1			
			D1	D29	D1	D8	D29	D181
	Exclusion code	PPS01FL	FAS01FL	FAS02FL	FAS03FL	FAS04FL	FAS05FL	FAS06FL
100	Study vaccine not administered AT ALL	EXC						
110	Serological results are not available	EXC						
110.1	Serological results are not available for hSBA	EXC						
110.2	Serological results are not available for ELISA	EXC	None	None	EXC	EXC	EXC	EXC
112	Obvious deviation from Laboratory Manual or error in laboratory data	EXC						
112.1	Incoherence between CRF and CLS database in terms of sample availability (e.g. sample not collected but result is available)	EXC						
112.2	Label error of blood samples that could not be resolved	EXC						
112.3	Wrong handling of laboratory samples with impact on the results (e.g. critical deviations during storage at sites or shipment but sample was tested)	EXC						

19 JAN 16 Final Version 1.0

Confidential

Page 26 of 59

120	Randomization failure	EXC	EXC	EXC	EXC	EXC	EXC	EXC
120.1	Subject randomized to the wrong strata	EXC	None	None	None	None	None	None

BCDM-14 TEMP 01 / Atlas No. 296412

PD code	PD Description	PPS	FAS-2		FAS-1			
			D1	D29	D1	D8	D29	D181
	Exclusion code	PPS01FL	FAS01FL	FAS02FL	FAS03FL	FAS04FL	FAS05FL	FAS06FL
120.2	Subject received another vaccine than allocated (Actual Arm different from Planned Arm)	EXC	None	None	None	None	None	None
130	Randomization code was broken	EXC	None	None	None	None	None	None
140	Vaccination not according to protocol	EXC	None	None	None	None	None	None
140.1	Administration of temperaturedeviated vaccine	EXC	None	None	None	None	None	None
140.2	Administration of expired vaccine	EXC	None	None	None	None	None	None
140.3	Administration of only part of the study vaccine	EXC	None	None	None	None	None	None
140.6	Route of study vaccine administration wrong or unknown	EXC	None	None	None	None	None	None
140.7	Site / side of study vaccine administration wrong or unknown	EXC	None	None	None	None	None	None

19 JAN 16 Final Version 1.0

Confidential

Page 27 of 59

140.8	Administration not according to protocol for other reasons specified by the investigator	EXC	None	None	None	None	None	None
150	Administration of forbidden vaccine	EXC	None	None	None	None	None	None
200	Subject did not meet entry criteria	EXC	None	None	None	None	None	None
220	Subject had contraindication for a subsequent study vaccination but was vaccinated	EXC	None	None	None	None	None	None

BCDM-14 TEMP 01 / Atlas No.
296412

PD code	PD Description	PPS	FAS-2		FAS-1			
			D1	D29	D1	D8	D29	D181
	Exclusion code	PPS01FL	FAS01FL	FAS02FL	FAS03FL	FAS04FL	FAS05FL	FAS06FL
230	Administration of forbidden medication	EXC	None	None	None	None	None	None
240	Underlying medical condition forbidden by the protocol	EXC	None	None	None	None	None	None
250	Concomitant infection related to the vaccine which may influence immune response	EXC	None	None	None	None	None	None
260	Did not comply with study vaccination schedule	EXC	None	None	None	None	None	None
270	Did not comply with blood draw schedule	EXC	None	None	None	None	None	None

Version No. 5 / Version Date: April 30, 2015

19 JAN 16 Final Version 1.0

Confidential

Page 28 of 59

19 JAN 16 Final Version 1.0		Confidential						
		EXC	None	None	None	None	None	None
270.1	Day 1 blood draw performed out of planned visit window	EXC	None	None	None	None	None	None
270.2	Day 8 blood draw performed out of planned visit window	EXC	None	None	None	None	None	None
270.3	Day 29 blood draw performed out of planned visit window	EXC	None	None	None	None	None	None
270.4	Day 181 blood draw performed out of planned visit window	EXC	None	None	None	None	None	None

FAS = Full Analysis Set; PPS=Per Protocol Set; EXC = excluded from this analysis set.

BCDM-14 TEMP 01 / Atlas No. 296412

Version No. 5 / Version Date: April 30, 2015

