6. DETERMINATION OF PROTOCOL DEVIATIONS

6.1 Definition of Protocol Deviations

Major (Clinical Study Report (CSR) reportable) protocol deviations (PDs) are defined in accordance with ICH E3 as important PDs related to study inclusion or exclusion criteria, conduct of the trial, subject management or subject assessment resulting in the potential to jeopardize the safety or rights of the trial subjects or the scientific value of the trial.

All reportable PDs will be evaluated before unblinding and classified according to ICH into the following five categories:

- Subject developed withdrawal criteria during the study but was not withdrawn:
 - Underlying medical condition forbidden by the protocol or which may influence immune response.
 - Subject received wrong vaccine or incorrect dose.
 - Study vaccine was not administered at all.
 - Vaccine administration not according to protocol.
 - Randomization failure.
- Subject took an excluded concomitant medication:
 - Administration of concomitant vaccine(s) forbidden in the protocol.
 - Administration of any medication forbidden by the protocol.
- Subject randomized and did not satisfy the entry criteria:
 - Subject did not meet entry criteria.
- Deviations from key study procedures:
 - Randomization code was broken.
 - Subject did not provide any post-vaccination safety data.
 - Subject did not comply with blood draw schedule.
 - Serological results not available post-vaccination.
 - Obvious incoherence, abnormal serology evolution or error in data.

Major (CSR reportable) PD will lead to exclusion of the subject or part of the subject's data from at least one analysis set.

The number of subjects in any and by PD category will be summarized by dosage and overall and individual subject listings will be provided in an appendix.

Prior to unblinding, designated PXL and Sponsor staff will develop a memo that describes the PDs that lead to exclusions from analysis sets. This memo will be signed off by at least the Biostatistician and the Cluster Physician and will be included in the trial master file.

Prematurely terminating study participation for reasons such as withdrawal of consent or occurrence of adverse events (including death) is not considered as a PD. The missing assessments that should have otherwise been collected for that subject later in the study are also not considered as a PD.

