6.2 Determination of Protocol Deviations

Prior to unblinding, a set of listings will be provided to the Cluster Physician and the Clinical Trial Leader (CTL) for review according to PXL SOP-EP.BS-WW-008-01.

The listings will be programmed following the list presented in table in section 7.3.8, and specifically using the PD codes specified in the first column. In addition, PDs will be evaluated during periodic review meetings as described in the Protocol Deviations Manual.

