8.2.2 Immunogenicity Data

Imputation methods will not be used. Primary, secondary, and exploratory objectives will be analyzed using the PPS. The primary objectives will also be analyzed using the FAS as a measurement of the robustness of the findings.

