11.2 Primary Objectives Analysis

The primary immunogenicity endpoints are the GMTs measured by hSBA directed against MenC from samples collected on Day 1 (baseline, before vaccination) and Day 29 as well as the GMR of the titers (Day 29 / Day 1).

The primary immunogenicity analyses will be based on the PPS on Day 29. The primary endpoints will also be assessed using the FAS as a sensitivity analysis

Geometric Mean Titers

The logarithmically (base 10) transformed antibody titers will be modeled using an analysis of covariance (ANCOVA) model with a qualitative factor for the dosage of the LHD153R adjuvant (0, 12.5, 25, 50 or 100 µg) and log (base 10) pre-vaccination titer as a covariate. The adjusted GMT and the two-sided, 95% confidence intervals (CIs) of the GMT will be calculated based on this model as will the ratio of GMTs and corresponding CIs.

The adjusted GMT and two-sided 95% CIs will be constructed by exponentiation (base 10) of the least square means of the logarithmically transformed (base 10) antibody titer. The ratio of GMTs (LHD153R adjuvant dosage minus Men C control), and corresponding two-sided 95% CIs, will be constructed by exponentiation (base 10) of the least square differences obtained from this model. The model can be written as:

$$\log_{10} (y_{ik}) = \mu + \alpha_i + \beta x_{ik} + \varepsilon_{ik}$$

where μ represents a common overall mean, α_i represents the adjuvant dose group i effect, β represents the common slope for the \log_{10} pre-vaccination titer, x_{ik} for subject k in adjuvant dose group i , and ε_{ik} represents random error for subject k in adjuvant dose group i .

The following SAS[□] code will be used for this ANCOVA model:

```
ODS OUTPUT DIFFS=D_SET
      LSMEANS=L_SET;
PROC MIXED ORDER=data;
  CLASS adj_dosage;
  MODEL log_titer=adj_dosage log_pre/ddfM=KR;
  LSMEANS adj_dosage /DIFF CL;
RUN;
```

where:

ADJ_DOSAGE: adjuvant dosage (0, 12.5, 25, 50 or 100 µg),

D_SET= dataset containing the ratio of LS means of the \log_{10} -transformed titers (the ratio of GMTs and the two-sided 95% CIs will be constructed by exponentiation -base 10-, only the values where _adj_dosage=0 will be used),

LOG_PRE= \log_{10} -transformed value of pre-vaccination titer,

LOG_TITER=log10-transformed value of titer on Day 29,

L_SET=dataset containing the LS means of the log10-transformed titer for each adjuvant dosage (the adjusted GMT and two-sided 95% CIs will be constructed by exponentiation -base 10-).

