14. INTERIM ANALYSIS

14.1 Interim Analysis

A safety and immunogenicity interim analysis for the selection of an LHD153R adjuvant dosage will be performed based on the data collected through Day 29 from subjects enrolled in all cohorts. This analysis will be performed by personnel not involved in study decisions. The results will be unblinded at the group level thereby preserving the blind for individual subjects. No adjustment to the overall alpha will be performed as the data collected subsequent to this analysis involve secondary and exploratory endpoints.

The interim analysis is to be considered final with regards to the Immunogenicity and Safety Tables up to Day 29.

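### One per-protocol flag covers all visits and both assays, so a Day 8 or Day 181 window deviation or a missing ELISA result removes a subject from the primary Day 29 hSBA analysis

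*SAP*

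**What the plan says.** Table 7.7-2 maps each protocol deviation code to the immunogenicity sets. The per-protocol set has one column (PPS01FL). The FAS has six (FAS01FL to FAS06FL), split by visit. The footnote defines EXC as exclusion from the set in that column. PPS01FL is EXC for 110.2 ("Serological results are not available for ELISA"), for 270.2 (Day 8 draw outside its window) and for 270.4 ("Day 181 blood draw performed out of planned visit window").

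The text around the table:

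- Section 7.5 defines one PPS with no visit or assay index. One condition is "Have no major protocol deviations leading to exclusion (see section 6.2").
- Section 6.2 has the deviation listings programmed from a table, "specifically using the PD codes specified in the first column". It places that table in section 7.3.8, which is not in the SAP text. The only tables with deviation codes are in section 7.7.
- Section 6.1 says a major deviation "will lead to exclusion of the subject or part of the" subject's data, from at least one set.
- Section 8.2.2: "Primary, secondary, and exploratory objectives will be analyzed using the PPS".
- Section 11.2 defines the primary endpoint by hSBA on Days 1 and 29, and adds: "The primary immunogenicity analyses will be based on the PPS on Day 29".
- Section 14.1: "The interim analysis is to be considered final with regards to the Immunogenicity and Safety Tables up to Day 29".

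**The concern.** The primary comparison needs a valid hSBA titre on Day 1 and on Day 29. A late Day 8 draw, a late Day 181 draw or a failed ELISA says nothing about either titre. Yet each one sets the only per-protocol flag to exclude, just as an out-of-window Day 29 draw (270.3) does. With 16 subjects per group, every needless exclusion costs precision in the analysis on which dosage selection rests.

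Code 270.4 also raises a timing problem. The Day 29 tables are declared final at an interim that is unblinded at group level, and for many subjects their Day 181 status cannot be known by then.

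The FAS sensitivity analysis is the natural safeguard, but section 7.4 and Table 7.7-2 give the FAS labels different meanings.

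**Working it through.** The plan states no figure on this point, so there is none to reproduce. The check is a reading of the table followed by simple arithmetic.

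**1. Table rows against the primary endpoint (hSBA, Days 1 and 29)**

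| Code | Records | PPS01FL | FAS01FL–02FL (D1, D29) | FAS03FL–06FL (D1, D8, D29, D181) | Affects primary data? |
|---|---|---|---|---|---|
| 110.2 | ELISA result missing | EXC | None | EXC | No |
| 270.2 | Day 8 draw out of window | EXC | None | None | No |
| 270.3 | Day 29 draw out of window | EXC | None | None | Yes |
| 270.4 | Day 181 draw out of window | EXC | None | None | No |

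Row 110.2 treats the two FAS blocks differently. The table therefore separates assays for the FAS but not for the PPS.

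**2. FAS labels**

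| Label | Section 7.4 | Table 7.7-2 |
|---|---|---|
| FAS-1 | Days 1 and 29 | D1, D8, D29, D181 |
| FAS-2 | Days 1 and 8 | D1, D29 |
| FAS-3 | Day 181 | absent |

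Sections 8.2.2 and 11.2 name only the FAS, without a number. A programmer who takes FAS-1 from section 7.4 and then uses the table's FAS-1 flags would apply the ELISA exclusion to the hSBA sensitivity analysis.

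**3. Timing**

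181 − 29 = 152 days. Entry is staggered, so some early-cohort Day 181 draws may precede the interim. Unless the interim waits about five months after the last Day 29 visit, late-enrolled subjects have no 270.4 status at that point. A 270.4 deviation recorded later would either change a Day 29 set already declared final or leave the table unfollowed. If none occurs, the sets match.

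**4. Cost per subject lost (no rate assumed)**

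Group size is 16 (Table 1; the control is 4 per cohort × 4 cohorts). The residual SD is held fixed.

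- Interval for the group's log GMT, factor √(16/n): √(16/15) = 1.033; √(16/14) = 1.069; √(16/13) = 1.109.
- Interval for its ratio to a control of 16, factor √[(1/n + 1/16)/(2/16)]: 1.017, 1.035 and 1.056 for n = 15, 14 and 13.

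**5. Illustration under assumed rates**

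The SAP gives no deviation rates. Assume *k* independent codes, each at rate *p*, in every group. Share lost = 1 − (1 − p)^k; interval factor = (1 − p)^(−k/2).

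| Assumed p | All three codes (k = 3): lost; n left of 16; factor | Window codes only (k = 2): lost; n left of 16; factor |
|---|---|---|
| 2% | 5.9%; 15.1; 1.03 | 4.0%; 15.4; 1.02 |
| 5% | 14.3%; 13.7; 1.08 | 9.8%; 14.4; 1.05 |
| 10% | 27.1%; 11.7; 1.17 | 19.0%; 13.0; 1.11 |

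With t quantiles on the reduced residual degrees of freedom, the three-code factors are 1.032, 1.083 and 1.179, each within 0.01 of those shown.

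**The case against.** The strongest reply is that a visit-specific PPS was probably intended. Section 7.7 introduces its tables as mock-ups. Section 6.2 speaks of review listings, not automatic exclusions, and the exclusions themselves are fixed in a memo signed before unblinding. Section 7.5 builds the PPS from the FAS, which section 7.4 indexes by visit. Section 11.2 ties the PPS to Day 29, section 6.1 allows part of a subject's data to be removed, and code 270 is split by visit, which would have little point if any one of the subcodes removed the subject everywhere. All of this bears on intent. None of it is a rule that limits a code to its visit or assay, and no other place in the SAP maps codes to sets. The memo therefore has no rule to apply except the table, which points the other way.

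Second, because section 14.1 makes the Day 29 tables final, a later Day 181 deviation should not reopen them. That is the sensible reading, but it means departing from the table, and the SAP does not say so.

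Third, the practical loss may be small, and this largely stands. Both assays use one serum draw, so only ELISA-only failures count under 110.2. Code 270.4 touches only continuing subjects drawn outside the 7-day window, because section 6.1 does not count assessments missed after early termination as deviations. The low end of the assumed rates is therefore more plausible for 110.2, and the 10% row is an upper illustration.

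Fourth, the FAS analysis retains the window-deviation subjects in every column, and those lacking only an ELISA result in the D1/D29 block. That is correct provided the right block is used, which the conflicting labels leave open.

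**Conclusion.** The point holds as a defect in the written rule. Table 7.7-2, read as it stands, removes subjects with valid hSBA data on Days 1 and 29 from the primary per-protocol analysis for reasons unrelated to that endpoint, and the phrases suggesting otherwise are not carried into any flag or rule. It does not show that subjects will in fact be dropped.

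The consequence is lost precision and an ambiguous Day 29 set. The firm figures are those per subject lost from a group of 16. The percentages in step 5 rest on assumed equal, independent rates and should be read only as a range. The FAS label conflict and the dead reference to section 7.3.8 are smaller matters, but the first weakens the safeguard that would otherwise contain the problem. This should be fixed; confidence in the reading of the table is high.

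**What to change.** - Replace PPS01FL with flags by assay and visit: hSBA Day 8, Day 29 and Day 181; ELISA Day 8, Day 29 and Day 181.
- For the hSBA Day 29 flag, set 110.2, 270.2 and 270.4 to None, and apply each code only to its own visit or assay.
- State that the Day 29 PPS is locked in the signed deviation memo before the interim unblinding and is not reopened for later deviations.
- Align the FAS-1, FAS-2 and FAS-3 labels in Table 7.7-2 with section 7.4, and name the FAS used for the primary sensitivity analysis in sections 8.2.2 and 11.2.
- Point section 6.2 to section 7.7.

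The cost is SAP wording and a few extra analysis flags; no new data are needed. With these changes the three codes remove no one from the primary analysis.

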8. GENERAL ISSUES FOR STATISTICAL ANALYSES

8.1 Adjustment for Covariates

Section 11.2 describes the statistical model and all adjustments for covariates.

8.2 Handling of Dropouts, Missing Data

First-line analyses will be without missing values.

8.2.1 Safety Data

To minimize the effect of dropouts and missing data, the study period will be divided into time intervals for statistical analysis of safety.

Unsolicited adverse events: these events will be reported from the date of signed informed consent to Day 14 and from Day 15 to study termination (for SAEs, Medically Attended AEs, NOCDs and AESIs).

Solicited adverse events, the solicited study period (Days 1-14) after vaccination will be divided into these intervals: 30 min, Days 1-4 (without 30 min), Days 5-8, Days 1-8 (without 30 min), Days 8-14 and Days 1-14 (without 30 min).

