7.3 Safety Set

Solicited Safety Set

All subjects in the All Exposed Set who:

- Provide post vaccination local or systemic solicited adverse event data. Unsolicited Safety Set

All subjects in the All Exposed Set who:

- Have post-vaccination unsolicited adverse event data.

Overall Safety Set

All subjects who are in the solicited safety set and/or in the unsolicited safety set.

Subjects providing only 30 minutes postvaccination safety data will be reported separately in a 30 minute postvaccination safety analysis and excluded from all other safety analysis.

In case of vaccination error, subjects will be analyzed as "treated" (i.e., according to the vaccine a subject receives, rather than the vaccine to which the subject is randomized).

If a subject is unblinded during the study, he/she will be included in all safety sets.

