13.1.1 Safety Completeness Analysis

Solicited adverse events

The safety completeness analysis on solicited adverse events aims to identify subjects who completed diary cards, irrespective of severity. The analysis will show the number of subjects with *valid data* by solicited adverse event and time point. *Valid data* in the context of the safety completeness analysis are all data entered in the diary card (including implausible values) except “Not done/unknown”.

Four summaries will be produced:

1. The frequencies of subjects who provide diary cards by dosage group.
2. For each solicited adverse event, the frequencies of subjects with *valid data* will be presented by dosage group and time point: 30 minutes post-vaccination and by day for Days 1 through 14.
3. For each type of solicited adverse event (local, systemic) and indicators of solicited adverse events, such as analgesic use, the frequencies of subjects with *valid data* by vaccine group, aggregated over time points: Days 1-14 (without 30 minutes).
4. For each solicited adverse event, the frequencies of subjects with *valid data* by vaccine group, aggregated over time points: Days 1-14 (without 30 minutes).

For the corresponding percentages, the denominator will be the respective numbers of exposed subjects, i.e., subjects who received a vaccination and were still in-study for that time point or time interval, irrespective of whether or not a diary card was present.

All analyses will be based on the ‘as treated’ analysis set.

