- Vomiting: ER visit or hospitalization for hypotensive shock
- Diarrhea: ER visit or hospitalization
- Generalized Myalgia: ER visit or hospitalization
- Generalized Arthralgia: ER visit or hospitalization
- Headache: ER visit or hospitalization,
- Fatigue: ER visit or hospitalization,
- Generalized Rash, ER visit or hospitalization Urticaria: ER visit or hospitalization.

Body temperature will be broken down by route of measurement according to the recommendations of the Brighton collaboration and will be summarized according to the 3 schemes described below:

- by 0.5 °C increments: <36.0 , ≥ 36.0 - <36.5 , ≥ 36.5 - <37.0 , ≥ 37.0 - <37.5 , ≥ 37.5 - <38.0 , ≥ 38.0 - <38.5 , ≥ 38.5 - <39.0 , ≥ 39.0 - <39.5 , ≥ 39.5 - <40.0 , ≥ 40.0 °C
- by 1.0 °C increments: <36.0 , ≥ 36.0 - <37.0 , ≥ 37.0 - <38.0 , ≥ 38.0 - <39.0 , ≥ 39.0 - <40 , ≥ 40 °C

- $<38.0, \geq 38.0$ °C

Fever, defined as a body temperature of ≥ 38 °C irrespective of route of measurement, will be considered a systemic adverse event.

The analyses will encompass summaries of the data on five levels:

1. Daily reports of subjects with solicited adverse events.
2. Time of first onset of solicited adverse events (excluding 30 min post-vaccination).
3. Solicited adverse events, maximum event severity by event and time interval.
4. Number of days with solicited adverse events.
5. Solicited adverse events and indicators of solicited adverse events, occurrence of at least one event by category (local, systemic) and time interval.

For each of the time intervals presented in the summaries, only subjects with at least one plausible observation for the solicited adverse events will be included.

Level 1: Daily reports of solicited adverse event

For each time interval, only subjects with at least one plausible observation for the solicited adverse event will be included in the analysis. For each time interval, the number and percent of subjects will be presented by dosage group, solicited adverse event and overall.

Level 2: Time of first onset of solicited adverse events

The **time of first onset** of a solicited adverse event experienced by each subject is the time point at which the event first occurred. For erythema, induration and swelling, a threshold of ≥ 25 mm will be used. The summary will provide the frequencies and percentages of subjects with first onset of each solicited adverse events by dosage group and time point.

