13.3 Unsolicited Adverse Events

All the unsolicited adverse events occurring during the study, judged either as probably related, possibly related, or not related to vaccination by the investigator, will be recorded.

The original verbatim terms used by investigators to identify adverse events in the Case Report Forms (CRFs) will be mapped to preferred terms using the MedDRA dictionary. The unsolicited adverse events will then be grouped by MedDRA preferred terms into frequency tables according to system organ class. All reported adverse events, as well as adverse events judged by the investigator as at least possibly related to study vaccine, will be summarized by dosage group, according to system organ class and preferred term within system organ class. When an unsolicited adverse event occurs more than once for a subject, the maximal severity and strongest relationship to the dosage group will be counted.

Only treatment-emergent adverse events will be analyzed, i.e., excluding those after a subject has given informed consent but before vaccination. The selection of unsolicited adverse events and the assignment to time intervals (Days 1-14 after vaccination, and from Day 15 post vaccination until study termination) will be done by day of onset and not by days ongoing/persisting.

The analysis of unsolicited adverse events comprises the following categories:

- Any unsolicited adverse event.
- Possibly or probably related unsolicited adverse events.
- Unsolicited adverse events leading to death.
- Serious adverse events.
- Possibly or probably related serious adverse event.
- Unsolicited adverse events leading to premature withdrawal from study.
- Medically attended adverse events.
- Adverse events of special interest (AESI).
- New onset of chronic disease (NOCD).

Data listings of all adverse events will be provided by subject. In addition, adverse events in the categories above will be provided as listed data.

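### One Unsolicited Safety Set serves both follow-up intervals, so late unsolicited-event percentages are diluted wherever subjects drop out

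*SAP*

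**What the plan says.** Section 8.2.1 gives the reason for splitting follow-up: "To minimize the effect of dropouts and missing data, the study period will be divided into time intervals for statistical analysis of safety". Unsolicited events are reported "from the date of signed informed consent to Day 14 and from Day 15 to study termination", the later interval being for SAEs, medically attended AEs, NOCDs and AESIs.

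For solicited events the SAP carries this through to the denominator. Table 7.7-1 has four interval flags (SSS01FL to SSS04FL), and section 13.2 says that for each interval "only subjects with at least one plausible observation for the solicited adverse events will be included".

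For unsolicited events it does not:

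- Section 7.3 defines one Unsolicited Safety Set: exposed subjects who "Have post-vaccination unsolicited adverse event data". No interval is named.
- Table 7.7-1 gives that set one flag, SSU10FL. It is lost only under code 100 (vaccine not administered) or code 115, described as "Subject did not provide any post-vaccination unsolicited safety data".
- Section 13.3 says that the assignment of events to the two intervals "will be done by day of onset and not by days ongoing/persisting". It sets no condition that the subject was still in the study.
- Section 6.1 does not treat early termination as a protocol deviation, and adds: "The missing assessments that should have otherwise been collected for that subject later in the study are also not considered as a PD". No deviation code therefore removes an early leaver from the later interval.

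**The concern.** A subject who is no longer observed cannot contribute an event. If that subject stays in the denominator, the percentage treats absence of observation as absence of an event. Splitting follow-up at Day 14 does not cure this for the later interval unless that interval has its own at-risk denominator or uses observation time.

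The later interval runs to Day 366 and carries the long-term safety information on a new adjuvant: SAEs, AESIs, NOCDs and medically attended events. Comparing safety with the control vaccine is a primary objective (section 2.1). Dilution lowers the percentage in any group with dropout and lowers it more where dropout is heavier, so unequal dropout would distort the comparison across dosage groups.

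**Working it through.** The SAP states no figure on this point, so there is none to reproduce. The check has two parts: tracing one subject through the set definitions, and sizing the effect.

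**Tracing an early leaver.** Take a subject vaccinated on Day 1 who provides unsolicited data at Day 4 and Day 8 and leaves on Day 10.

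1. Code 100 does not apply, because the vaccine was given.
2. Code 115 does not apply, because some unsolicited data exist. SSU10FL is kept.
3. Leaving early is not a deviation (6.1), so no further exclusion follows.
4. Section 13.3 allocates events, not subjects, to intervals.

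The subject is therefore in the only unsolicited set defined and has no time at risk from Day 15. Two kinds of early leaver fall outside this: those with no unsolicited data, excluded by code 115, and those with only 30-minute data, whom section 7.3 reports separately.

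**Inputs for the size.** Group size is 16: dosage groups B to E have 16 each, and group A has 4 in each of 4 cohorts (section 3, Table 1). The number *d* who leave before Day 15 is not in the SAP and is assumed.

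**Formulas.** With *x* late events, the percentage is *x*/16 under the single set and *x*/(16 − *d*) among those still observed at Day 15. The ratio is (16 − *d*)/16, a relative understatement of *d*/16. For zero events the two-sided 95% Clopper-Pearson upper limit is 1 − 0.025^(1/*n*).

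| *d* (assumed) | *n* at Day 15 | One late event, single set | One late event, at-risk set | Relative understatement | Upper limit for 0 events, *n* = 16 | Upper limit for 0 events, at-risk *n* |
|---|---|---|---|---|---|---|
| 0 | 16 | 6.25% | 6.25% | 0% | 20.6% | 20.6% |
| 1 | 15 | 6.25% | 6.67% | 6.25% | 20.6% | 21.8% |
| 2 | 14 | 6.25% | 7.14% | 12.5% | 20.6% | 23.2% |
| 4 (extreme) | 12 | 6.25% | 8.33% | 25% | 20.6% | 26.5% |

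The upper limits only show how much a zero count can rule out; section 13 does not plan confidence limits for unsolicited events.

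**Losses after Day 15.** Day 15 to Day 366 is 366 − 15 + 1 = 352 days. A subject lost at Day 60 contributes 60 − 15 + 1 = 46 days, and 46/352 = 13% of the interval, yet counts as one full subject. An indicator of being in the study at Day 15 would leave this unchanged.

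**The case against.** Five points can fairly be made against the concern.

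- **Section 13.3 names no percentage denominator.** This stands. That an early leaver counts as event-free is an inference from the only set defined, not a sentence in the SAP. Section 8.2 also says that first-line analyses will be without missing values, and Table 7.7-1 is introduced as a mock-up that lacks flags for the solicited Days 1-8 and Days 1-14 intervals although both are analysed. Yet nowhere does the SAP supply another denominator for late unsolicited events.
- **The split does some work even with a common denominator.** This also stands. It keeps the Days 1-14 percentages free of later losses, and that interval is the one covering all unsolicited events. The stated aim is incompletely met for the later interval; it is not false.
- **Section 13.1.1 is not a counter-example.** Its denominator, "subjects who received a vaccination and were still in-study for that time point or time interval", belongs to the solicited diary completeness analysis and says nothing about how event percentages are formed. The contrast with solicited events rests on section 13.2 and the interval flags.
- **The dropout would be visible.** Section 9.1 reports discontinuations by dosage group and reason, observation time and attendance at each visit, and section 13.3 lists all events by subject. A reader could recompute a late percentage by hand, and no test between groups is planned for unsolicited events. This limits the harm but does not make the tabulated percentages right.
- **Dropout in the first two weeks may be small.** The SAP gives no figure. With none, the effect of early loss is nil.

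A reader might infer that the plan builds in an apparent safety benefit for the more reactogenic dosages. The documents do not support that. It would need heavier dropout at those dosages, which nothing in the SAP states. An apparent 15% against 20%, for example, needs an assumed 20% late risk and 4 of 16 subjects (25%) lost within two weeks in one group and none on control.

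**Conclusion.** The concern holds as a gap between the aim stated in 8.2.1 and the sets that are to deliver it. Under the only unsolicited set defined, late SAE, AESI, NOCD and medically attended AE percentages are diluted where subjects leave, both before Day 15 and between Day 15 and Day 366. For 1 or 2 early losses out of 16 the relative understatement is 6.25% or 12.5%, a modest effect. The conclusion assumes that SSU10FL is the denominator for the later interval, and the sizes rest on assumed losses. The Days 1-14 percentages are not affected by losses after Day 14. The change is worth making because it is cheap and uses data already collected, not because a material bias has been shown.

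**What to change.** 1. In Table 7.7-1, add a second unsolicited flag for Day 15 to termination, set for subjects still under observation on or after Day 15. State in section 13.3 that each interval's percentages use that interval's flag as denominator.
2. For the late categories, add events per person-year by dosage group. The flag alone does not handle losses after Day 15. Observation time is already summarised in section 9.1, and section 8.7.3 defines duration in the study from Visit 1; late time is that duration minus 14 days (366 − 14 = 352 for full follow-up).

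The cost is one flag, one table column and a rate calculation, with no new data. The denominators of the two intervals will differ slightly, and person-time rates will be imprecise with about 16 subjects per group, so they should be read as descriptive.
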